## 6.1 Description of study assessments

# Proprietary of MD Anderson Cancer Center

## Performance Status

The performance status of all patients will be graded according to the ECOG PS scale.

## Clinical Laboratory Tests

Clinical laboratory tests will be performed to assess eligibility for enrollment and will be repeated according to study calendar included in this section. Laboratory tests can be repeated more frequently, if clinically indicated.

## Symptoms and Toxicity Assessment

The symptoms and adverse events of all patients will be graded at scheduled intervals according to the NCI CTCAE, v4.03. Patients will be monitored continuously throughout the study for the occurrence of adverse events. Planned medical interventions will not be considered an adverse event.

## Radiology Assessments

CT chest (with/without abdomen/pelvis), PET-CT, and CT brain / MRI brain will be obtained according to Study Calendar included in this section. Response and progression will be evaluated in the study using the international criteria proposed by the RECIST committee, and will be performed by the MD Anderson radiology collaborator(s) on trial in a blind fashion.

## **7. Adverse Events Collection and reporting**

Timely, accurate, and complete reporting and analysis of safety information from clinical studies are crucial for the protection of subjects, investigators, and the sponsor, and are mandated by regulatory agencies worldwide.

The investigator (or physician designee) is responsible for verifying and providing source documentation for all adverse events and assigning the attribution for all adverse events for subjects enrolled.

### 7.1 Definitions

#### 7.1.1 Adverse events (AE)

An AE is any untoward medical occurrence in a patient administered a pharmaceutical product and which does not necessarily have a causal relationship with this treatment. An AE can therefore be any unfavorable and unintended sign (including a clinically significant abnormal laboratory finding, for example), symptom, or disease temporally associated with the use of an investigational study drug, whether or not considered related to the study drug. The term AE is used to include both serious and non-serious adverse events. For the purposes of this clinical study, AEs include events which are either new or represent detectable exacerbations of pre-existing conditions. The term "disease progression" should not be reported as an adverse event term. As an example, "worsening of underlying disease" or the clinical diagnosis that is associated with disease progression should be reported.

Adverse events may include, but are not limited to:

- Subjective or objective symptoms provided by the patient and/or observed by the Investigator or study staff including laboratory abnormalities of clinical significance.
- Any AEs experienced by the patient through the completion of final study procedures.

- AEs not previously observed in the patient that emerge during the protocol-specified AE reporting period, including signs or symptoms associated with the underlying disease that were not present before the AE reporting period
- Complications that occur as a result of protocol-mandated interventions (e.g., invasive procedures such as biopsies).

The following are NOT considered AEs:

- Pre-existing condition: A pre-existing condition (documented on the medical history CRF) is not considered an AE unless the severity, frequency, or character of the event worsens during the study period.
- Pre-planned or elective hospitalization: A hospitalization planned before signing the informed consent form is not considered an SAE, but rather a therapeutic intervention. However, if during the pre-planned hospitalization an event occurs, which prolongs the hospitalization or meets any other SAE criteria, the event will be considered an SAE. Surgeries or interventions that were under consideration, but not performed before enrollment in the study, will not be considered serious if they are performed after enrollment in the study for a condition that has not changed from its baseline level. Elective hospitalizations for social reasons, solely for the administration of chemotherapy, or due to long travel distances are also not SAEs.
- Diagnostic Testing and Procedures: Testing and procedures should not to be reported as AEs or SAEs, but rather the cause for the test or procedure should be reported.
- Asymptomatic Treatment Related Lymphocytosis: This event should also not be considered an AE. Patients with treatment-related lymphocytosis should remain on study treatment and continue with all study-related procedures.
- Any adverse event clearly attributable to disease progression

## 7.1.2 Severity criteria (Grade 1-5)

Definitions found in the Common Terminology Criteria for Adverse Events version 4.03 (CTCAE v4.03) will be used for grading the severity (intensity) of AEs. The CTCAE v4.03 displays Grades 1 through 5 with unique clinical descriptions of severity for each referenced AE. Should a patient experience any AE not listed in the CTCAE v4.03, the following grading system should be used to assess severity:

- Grade 1 (Mild AE) – experiences which are usually transient, requiring no special treatment, and not interfering with the patient's daily activities
- Grade 2 (Moderate AE) – experiences which introduce some level of inconvenience or concern to the patient, and which may interfere with daily activities, but are usually ameliorated by simple therapeutic measures
- Grade 3 (Severe AE) – experiences which are unacceptable or intolerable, significantly interrupt the patient's usual daily activity, and require systemic drug therapy or other treatment
- Grade 4 (Life-threatening or disabling AE) – experiences which cause the patient to be in imminent danger of death
- Grade 5 (Death related to AE) – experiences which result in patient death

## 7.1.3 Causality (Attribution)

The causality of SAEs (their relationship to all study treatment/procedures) will be assessed by the investigator(s) and communicated to Pfizer in accordance with the agreed process

- Not Related: Another cause of the AE is more plausible; a temporal sequence cannot be established with the onset of the AE and administration of the investigational product; or, a causal relationship is considered biologically implausible.
- Unlikely: The current knowledge or information about the AE indicates that a relationship to the investigational product is unlikely.
- Possibly Related: There is a clinically plausible time sequence between onset of the AE and administration of the investigational product, but the AE could also be attributed to concurrent or underlying disease, or the use of other drugs or procedures. Possibly related should be used when the investigational product is one of several biologically plausible AE causes.

These AEs will be reported as related if the investigator believes it is more likely than not that the investigational product caused the AE.

- Related: The AE is clearly related to use of the investigational product.

#### 7.1.4 Unexpected adverse events

An “unexpected” AE is an AE that is not listed in the Investigator's Brochure/package insert or is not listed at the specificity or severity that has been observed. For example, hepatic necrosis would be “unexpected” (by virtue of greater severity) if the Investigator's Brochure referred only to elevated hepatic enzymes or hepatitis. Similarly, cerebral thromboembolism and cerebral vasculitis would be “unexpected” (by virtue of greater specificity) if the Investigator's Brochure/package insert listed only cerebral vascular accidents. “Unexpected” also refers to AEs that are mentioned in the Investigator's Brochure as occurring with a class of drugs or as anticipated from the pharmacological properties of the drug, but are not specifically mentioned as occurring with the study drug under investigation.

### 7.2 Documenting and Reporting of Adverse Events and Serious Adverse Events by Investigators

Table7

Attribution	Grade 1	Grade 2	Grade 3	Grade 4	Grade 5
Unrelated	Phase I	Phase I	Phase I	Phase I	Phase I
			Phase II	Phase II	Phase II
				Phase III	Phase III
Unlikely	Phase I	Phase I	Phase I	Phase I	Phase I
			Phase II	Phase II	Phase II
				Phase III	Phase III
Possible	Phase I	Phase I	Phase I	Phase I	Phase I
	Phase II	Phase II	Phase II	Phase II	Phase II
		Phase III	Phase III	Phase III	Phase III
Probable	Phase I	Phase I	Phase I	Recommended Adverse Event Recording Guidelines	Phase I
	Phase II	Phase II	Phase II		Phase II
		Phase III	Phase III		Phase III
Definitive	Phase I	Phase I	Phase I	Phase I	Phase I
	Phase II	Phase II	Phase II	Phase II	Phase II
		Phase III	Phase III	Phase III	Phase III

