## 3. Study Design

### 3.1 Study Design

This is a Phase II, single center open label, study to determine the safety and efficacy of axitinib and avelumab combination in patients with recurrent or metastatic adenoid cystic carcinoma (ACC) with evidence of disease progression within 6 months prior to study enrollment.

Up to 30 patients will be treated with a combination of axitinib 5 mg orally twice a day and avelumab 10mg/kg intravenously every two weeks. A treatment cycle will be 28 days. Treatment will continue until disease progression, death, unacceptable toxicity or consent withdrawal.

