#### 7.2.2 Assessment of adverse events

Investigators will assess the occurrence of adverse events and serious adverse events at all subject evaluation time points during the study. All adverse events and serious adverse events whether volunteered by the subject, discovered by study personnel during questioning, detected through physical examination, clinically significant laboratory test, or other means, will be recorded. Each recorded adverse event or serious adverse event will be described by its duration (i.e., start and end dates), severity, regulatory seriousness criteria (if applicable), suspected relationship to the investigational product, and any actions taken.

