#### 7.2.3 Adverse Event Reporting Period

All AEs whether serious or non-serious, will be captured from the time signed and dated Informed Consent Form (ICF) is obtained until 30 days following the last dose of study drugs or until the initiation of alternative anticancer therapy. Progressive disease should NOT be reported as an

event term, but instead symptoms/clinical signs of disease progression may be reported. All Grade 3 – 5 adverse events, regardless of seriousness, severity, or presumed relationship to study drug, must be recorded using medical terminology in the source document. All records will need to capture the details of the duration and the severity of each episode, the action taken with respect to the study drug, investigator's evaluation of its relationship to the study drug, and the event outcome. Whenever possible, diagnoses should be given when signs and symptoms are due to a common etiology (e.g., cough, runny nose, sneezing, sore throat, and head congestion should be reported as "upper respiratory infection").

All deaths should be reported with the primary cause of death as the AE term, as death is typically the outcome of the event, not the event itself.

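### The AE recording rules conflict on low-grade events not attributed to treatment and on events due to progression, so all-causality AE counts depend on which rule is followed

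*Combined protocol and SAP*

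**What the plan says.** Section 3.1 fixes the phase, and so the entries of Table 7 that apply: "This is a Phase II, single center open label, study to determine the safety and efficacy of axitinib and avelumab combination".

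On which events are recorded:

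- **Table 7 (Section 7.2)** crosses five attribution levels with five grades and lists, in each cell, the trial phases to which recording applies. Its caption is "Recommended Adverse Event Recording Guidelines". In the Unrelated and Unlikely rows, grades 1 and 2 list Phase I only; Phase II first appears at grade 3.
- **Section 7.2.2** sets no limit by grade or attribution. Its sentence opens "All adverse events and serious adverse events whether volunteered by the subject, discovered by study personnel during questioning" and ends "detected through physical examination, clinically significant laboratory test, or other means, will be recorded".
- **Section 7.2.3** is equally broad: "All AEs whether serious or non-serious, will be captured from the time signed and dated Informed Consent Form (ICF) is obtained". It adds that grade 3 to 5 events go into the source document whatever their relationship to the drug.

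On events due to progression:

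- **Section 7.1.1, definition.** The term disease progression is barred, but as an example of what to use in its place, "the clinical diagnosis that is associated with disease progression should be reported". New signs or symptoms of the underlying disease also count as AEs.
- **Section 7.1.1, list of what is not an AE.** The last bullet is "Any adverse event clearly attributable to disease progression".
- **Section 7.2.3.** Reporting the signs and symptoms of progression is optional. Every death is to be entered under the cause that led to it, as an AE term.

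Safety and toxicity is a secondary objective (Section 2.2). Section 9.1 defines the safety population and Section 9.2 promises summary statistics and frequency tables. Neither says which AEs enter them.

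**The concern.** These instructions cannot all be followed. Two coordinators who each follow one part of Section 7 faithfully would build different safety datasets from the same patients.

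The trial has one arm, so its AE rates will be read on their own or beside outside data. A reader then needs to know whether an all-causality table is complete at low grades and whether it includes events due to the cancer. If grade 1 and 2 events are screened by the investigator's attribution before they are entered, an event left out may be hard to recover or re-attribute later.

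**Working it through.** The point concerns consistency of text. The plan states no figure to reproduce.

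**Step 1. Table 7 against Sections 7.2.2 and 7.2.3, for Phase II.**

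| Event | Table 7 | 7.2.2 and 7.2.3 | Agree? |
|---|---|---|---|
| Grade 1–2, Unrelated or Unlikely | not listed | recorded | No |
| Grade 1–2, Possible, Probable or Definitive | listed | recorded | Yes |
| Grade 3–5, any attribution | listed | recorded | Yes |

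The grid has 5 × 5 = 25 cells. Those without Phase II number 2 rows × 2 grades = 4. The Probable, grade 4 cell shows the caption in place of its entry. That looks like an effect of reading the PDF and is not counted as a conflict.

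Neither section refers to Table 7, and none of the three says which prevails. Table 7 also uses five attribution levels, while Section 7.1.3 defines four (Not Related, Unlikely, Possibly Related, Related), so the grid cannot be applied directly.

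**Step 2. Progression-related events.**

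| Place | Status of the event |
|---|---|
| 7.1.1, definition | to be reported, under the diagnosis or as worsening disease |
| 7.1.1, exclusion list | not an AE, if clearly due to progression |
| 7.2.3 | signs and symptoms may be reported |
| 7.2.3, deaths | every death carries an AE term |

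The same event is thus required, excluded and optional. For a death from the cancer, the exclusion bullet and the rule on deaths point in opposite directions.

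**Step 3. Which results move.**

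- All-causality counts at grades 1 and 2 move with the reading of Table 7.
- All-causality counts at any grade, including grade 5, move with the reading of the progression rules.
- Treatment-related counts do not move through Table 7: events judged possible or higher are listed for Phase II at every legible grade.
- The toxicity stopping rule (Section 9.2, Tables 8 and 9) counts events in the first 4 weeks attributed to one or both agents, mostly grade 3 or worse. These are recorded under either reading.
- The objective response rate does not use AE data.

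**Step 4. Can the loss under Table 7 be sized?** Let A be the all-causality rate of an event and R its treatment-related rate, as proportions of patients. If every patient whose only episodes were unrelated or unlikely had them at grade 1 or 2, the share of all-cause cases lost is at most 1 − R/A. For the combination, Table 2 gives R but nothing in the documents gives A by event. A can lie anywhere from R to 100%:

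- diarrhoea, R = 32/55 = 58%: from 0 to 1 − 58/100 = 42%;
- nausea, R = 11/55 = 20%: from 0 to 1 − 20/100 = 80%.

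These ranges also assume that the rates in the renal cancer study behind Table 2 carry over. They are too wide to support any single figure.

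**The case against.** The best defence is that Table 7 is only a recommendation, while Sections 7.2.2 and 7.2.3 are worded as obligations, so the obligations should win. That is a reasonable reading. The grid may also have been meant for CRF entry as opposed to source records. The protocol says neither, and Section 8 does not say which AEs go into the electronic forms, so the contradiction stands.

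Three further points for the defence hold in whole or in large part. Section 7.2.2 already requires the suspected relationship for each recorded event, so attribution is a separate item now. Section 7.1.1 supplies usable wording for a death from the cancer (worsening of the disease, or the associated diagnosis), so barring the term progression does not leave such a death uncodable; what stays open is whether it is an AE at all. And no decision rule in Section 9 depends on the disputed events.

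Two stronger readings are tempting and should not be drawn.

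- *That Table 7 would lose about 45% to 70% of common events.* A reader might infer this from the avelumab monotherapy rates in Section 1.2.1, all-cause against treatment-related: fatigue 1 − 17.7/32.4 = 45%, diarrhoea 1 − 7.1/18.9 = 62%, nausea 1 − 8.6/25.1 = 66%, decreased appetite 1 − 5.2/18.4 = 72%. Those rates belong to one drug. At the combination's own treatment-related rate, a 62% loss of diarrhoea cases is impossible, since the ceiling is 42%.
- *That the combination would look safer than axitinib alone.* Setting treatment-related rates for the combination (Table 2) beside all-causality rates for axitinib (Table 1) gives no consistent direction: nausea 20% against 32.6% and decreased appetite 24% against 40.0%, but diarrhoea 58% against 55.0% and dysphonia 47% against 31.1%. Section 9 plans no comparison with Table 1.

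**Conclusion.** The concern holds as an inconsistency in the recording rules. Its reach is limited to all-causality AE counts for a descriptive secondary objective in at most 30 patients: grade 1 and 2 events judged Unrelated or Unlikely (4 of 25 cells) through Table 7, and events of any grade through the progression rules, including the status of deaths from the cancer. How many events are at stake cannot be derived from the documents.

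The conclusion rests on reading the legible cells of Table 7 as printed and on the absence of any statement of precedence. The finding that treatment-related rates are unaffected assumes that related means possible or higher. The point merits correction because the rules are incompatible and the repair is cheap; it does not touch the primary conclusion or safety stopping.

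**What to change.** 1. **One recording rule.** For example, state in Section 7.2 that all AEs of any grade and attribution are entered in the CRF throughout the AE period, using the relationship field that Section 7.2.2 already requires. Remove Table 7 or state its purpose. If it stays, align its attribution levels with Section 7.1.3.
2. **One rule for progression-related events.** Reconcile the exclusion bullet in Section 7.1.1 with the definition in the same section and with Section 7.2.3. Flag as due to progression those events that are recorded, and say whether a death from the cancer carries an AE term.
3. **Section 9.** State which AEs are tabulated, including how flagged events are handled.

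The cost is wording in Sections 7.1.1, 7.2 and 9. The downside is extra low-grade AE data entry for at most 30 patients.

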#### 7.2.1 Serious Adverse Events (SAE) Reporting

It is the responsibility of the PI and the research team to ensure serious adverse events are reported according to the Code of Federal Regulations, Good Clinical Practices, the protocol guidelines, the sponsor's guidelines, and Institutional Review Board policy.

## Proprietary of MD Anderson Cancer Center

An adverse event or suspected adverse reaction is considered “serious” if, in the view of either the investigator or the sponsor, it results in any of the following outcomes:

- Death
- A life-threatening adverse drug experience – any adverse experience that places the patient, in the view of the initial reporter, at immediate risk of death from the adverse experience as it occurred. It does not include an adverse experience that, had it occurred in a more severe form, might have caused death.
- Inpatient hospitalization or prolongation of existing hospitalization
- A persistent or significant disability/incapacity or substantial disruption of the ability to conduct normal life functions.
- A congenital anomaly/birth defect.

Important medical events that may not result in death, be life-threatening, or require hospitalization may be considered a serious adverse drug experience when, based upon appropriate medical judgment, they may jeopardize the patient or subject and may require medical or surgical intervention to prevent one of the outcomes listed in this definition. Examples of such medical events include allergic bronchospasm requiring intensive treatment in an emergency room or at home, blood dyscrasias or convulsions that do not result in inpatient hospitalization, or the development of drug dependency or drug abuse (21 CFR 312.32).

All events occurring during the conduct of a protocol and meeting the definition of a SAE must be reported to the IRB in accordance with the institutional timeframes and procedures.

- Serious adverse events will be captured from the time of consent, until 30 days after the last dose of drug, unless the participant withdraws consent. Serious adverse events must be followed until clinical recovery is complete and laboratory tests have returned to baseline, progression of the event has stabilized, or there has been acceptable resolution of the event.
- Important medical events as defined above, may also be considered serious adverse events. Any important medical event can and should be reported as an SAE if deemed appropriate by the Principal Investigator.
- All events occurring during the conduct of a protocol and meeting the definition of a SAE must be reported to the IRB in accordance with the timeframes and procedures outlined in “The University of Texas M. D. Anderson Cancer Center Institutional Review Board Policy for Investigators on Reporting Serious Unanticipated Adverse Events for Drugs and Devices”.
- Unless otherwise noted, the electronic SAE application (eSAE) will be utilized for safety reporting to MDACC IRB.
- Serious adverse events will be captured from the time of the first protocol-specific intervention, until 30 days after the last dose of drug, unless the participant withdraws consent. Serious adverse events must be followed until clinical recovery is complete and laboratory tests have returned to baseline, progression of the event has stabilized, or there has been acceptable resolution of the event.

Reporting to Pfizer

The investigator primary responsibilities in the safety reporting are to identify and follow-up on Serious Adverse Events (SAEs) experienced by participants in the study and to forward the information to the local regulatory authorities and Pfizer, as required by local regulations (for regulatory reporting) and IIR agreement (for reporting to Pfizer).

The following reportable events must be submitted to Pfizer within 24 hours (or immediately for death or life-threatening events) using the provided Investigator-Initiated Research Serious Adverse Event Form (IIR SAE) with the Pfizer Reportable Events Fax Cover Sheet with each SAE submission.

- Serious Adverse Events
- Exposure during Pregnancy or Breastfeeding (even if not associated with an adverse event)
- Occupational exposure (even if not associated with an adverse event)
- Potential drug-induced liver injury (Hy's Law cases): These events are considered important medical events and should be reported as SAEs.
- Detailed guidance on the safety reporting is provided in the Safety Reporting Reference Manual (Appendix E).

Contact information for submission of reportable events to Pfizer:

Fax: Pfizer U.S. Clinical Trial Department, [contact].

Or

E-mail: [contact], specifying:

PROTOCOL:

SUBJECT:

SITE/PI:

SAE/ONSET:

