## 5.3 Safety assessment

For details see section 6(study calendar and procedures)

1. Blood chemistry and hematology assessments: must be performed at screening, prior to each avelumab dose, at end of treatment visit and at 30 days post-treatment safety follow-up.
2. Urine pregnancy test for women of childbearing potential must be performed at baseline and at least every month during treatment.
3. Free T4 and TSH must be performed at baseline and at least every 8 weeks during treatment and at end of treatment or 30 days post-treatment safety follow-up (if not performed in the previous 8 weeks).
4. Extended safety follow up: give the potential risk of immune-related toxicity, safety follow up will be performed up to 90 days after the last dose of avelumab administration. The extended follow up beyond 30 days after last avelumab administration may be performed either via a site visit or via a telephone call with subsequent site visit requested in case any concerns noted during the telephone call.

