# Proprietary of MD Anderson Cancer Center

EKG	X			
Echocardiogram	X	X 		
Urine analysis for proteinuria	X	X 		
Pregnancy Test (serum or urine) for all women of child bearing potential 	X	X 		
Radiology & Tumor Measurements 	X	X Every 8 weeks, ± 7 days		X
Biopsy	X If archived tissue not available			
Blood-based biomarkers	X 	X 		
Study Drug Compliance		X At each clinic visit		
Subsequent Anticancer Therapy				X
Survival Status				X

1 Written informed consent will be given by each patient prior to undergoing protocol specific evaluation and prior to receiving treatment

2 Chemistry profile includes: BUN, creatinine, sodium, potassium, carbon dioxide, magnesium, total bilirubin, alkaline phosphatase, aspartate aminotransferase, alanine aminotransferase, total protein, and serum phosphorus

3 Serum or urine pregnancy test will be obtained at baseline within 7 days prior to treatment and monthly during treatment in all women of child bearing age and again if clinically indicated

4 CT scan, PET CT scan of the chest/abdomen/pelvis and/or MRI of base of skull/orbit/face as clinically indicated. CT scan or MRI of the brain if clinically indicated

5 Long term follow-up will occur every 6 months by medical/clinical data review or phone contact

6 For patients who discontinue treatment due to reasons other than disease progression, tumor assessment will continue as per during the treatment schedule (i.e. radiology & tumor measurements every 8 weeks +/- 7 days).

7 Extended safety follow up: given the potential risk of immune-related toxicity, safety follow up will be performed up to 90 days after the last dose of avelumab administration. The extended follow up beyond 30 days after last avelumab administration may be performed either via a site visit or via a telephone call with subsequent site visit requested in case any concerns noted during the telephone call

8 Blood will be collected on at baseline (pre-treatment), day 7 (optional), day 15, prior to C3D1, and at progression (optional). Three categories of specimen will be collected: EDTA Vacutainer (checkpoint markers/CAFs): 10 mL = 1 x 10 mL; Streck CF-DNA BCT (ctDNA): 10 mL = 1 x 10 mL; and Sodium Heparin (immunoprofiling): 60 mL = 6 x 10 mL. All blood will be collected and processed by the Thoracic Research Team ([name] laboratory) according the institutional and laboratory standard operating procedures (SOPs).

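### Safety follow-up runs to day 90 after avelumab but the adverse event capture windows close at day 30, so recording of new events on days 31 to 90 depends on which section is followed

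*Combined protocol and SAP*

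**What the plan says.** Section 5.3 states that "safety follow up will be performed up to 90 days after the last dose of avelumab administration". Footnote 7 to Table 6 repeats this with its reason: "given the potential risk of immune-related toxicity, safety follow up will be performed up to 90 days after the last dose of avelumab administration". Contact after day 30 may be a visit or a telephone call.

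The explicit capture periods are shorter. Section 7.2.3 covers all adverse events, serious or not, from consent "until 30 days following the last dose of study drugs or until the initiation of alternative anticancer therapy". Section 7.2.1 gives the serious-event period twice, with the same end but different starts: "Serious adverse events will be captured from the time of consent, until 30 days after the last dose of drug", and later "Serious adverse events will be captured from the time of the first protocol-specific intervention, until 30 days after the last dose of drug".

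Other sentences carry no 30-day limit:

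- Section 7.2.1 on the IRB: "All events occurring during the conduct of a protocol and meeting the definition of a SAE must be reported to the IRB".
- Section 7.2.1 on the company: "The following reportable events must be submitted to Pfizer within 24 hours", with serious events on the list and no end date given.
- Section 7.2.2 has events assessed at every evaluation time point and recorded however they come to light.
- Section 7.1.1 counts as adverse events those occurring up to the end of the final study procedures.

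Section 9.1 says which patients enter the safety analysis, but not which event dates count.

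**The concern.** The protocol asks the site to keep looking for immune toxicity until day 90, while the section that defines the adverse event reporting period closes at day 30. Staff who work from Section 7.2.3 would leave out a new immune-related event first found at a day-50 call. Staff who work from Section 7.2.2 would record it. Both could cite the protocol.

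Safety and toxicity are a secondary objective (Section 2.2), to be described in about 30 patients. In a sample that small, a few events handled differently would visibly change the reported frequencies. The follow-up was lengthened for late immune toxicity, so that is the category most open to under-counting or uneven recording.

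**Working it through.** The plan states no figure for this point, so there is none to reproduce. The check is a comparison of the texts and a count of days.

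**Step 1. The rules side by side.**

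| Place | Covers | Ends | Clock |
|---|---|---|---|
| 5.3; Table 6 footnote 7 | Safety follow-up | Day 90 | Last avelumab dose |
| 7.2.3 | All adverse events | Day 30, or new anticancer therapy | Last dose of study drugs |
| 7.2.1 (both bullets) | Serious events | Day 30 | Last dose of drug |
| 7.2.1, IRB | Serious events | While the protocol is being conducted | None |
| 7.2.1, company | Serious events | Not stated | None |
| 7.2.2 | All events | Every evaluation time point | None |
| 7.1.1 | Adverse event definition | Final study procedures | None |
| Table 6, safety visit | Visit | Day 30 ± 7 | Last dose of study treatment |

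**Step 2. Two test cases**, both with the two drugs stopped on day 0.

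- *New non-serious immune-related event, first found at a day-50 contact.* Outside 7.2.3. Inside 7.2.2 if the contact counts as an evaluation time point, and inside 7.1.1 if the contact is a final study procedure. Nothing says which prevails.
- *New serious event on day 50.* Outside both capture bullets in 7.2.1, but inside the IRB sentence and not excluded by the company sentence. Here the fault is mainly conflicting wording, because a route to reporting exists.

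**Step 3. Length of the gap.** The two clocks can start on different dates. Section 5.9 allows one drug to continue when the other stops for toxicity, and Section 5.4 favours keeping axitinib. Let k be the number of days axitinib continues after the last avelumab dose. Reading the 30 days as running from the last dose of either drug, capture ends on day 30 + k after avelumab, so

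uncovered days = max(0, 90 − (30 + k)) = max(0, 60 − k).

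- k = 0: 60 days (60/90 = 67% of the follow-up)
- k = 30: 30 days (30/90 = 33%)
- k ≥ 60: 0 days

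If new anticancer therapy starts before the 30 days are up, and Section 7.2.3 is read as ending capture there, the gap for adverse events opens earlier.

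**Step 4. The safety visit.** Its window runs from day 30 − 7 = 23 to day 30 + 7 = 37. A visit held on days 31 to 37 is on schedule but falls after capture has closed.

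**Step 5. What is untouched.** The toxicity stopping rule in Section 9.2 uses the first 4 weeks (28 days) of treatment, and the primary endpoint is tumour response. Neither depends on events on days 31 to 90 after the last dose.

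**The case against.** The best reply is that the protocol already asks for these events. Section 5.3 and footnote 7 are the more specific text, written for immune toxicity. Sections 7.1.1 and 7.2.2 both reach contacts made after day 30, and Section 7.2.3 sets a period without telling anyone to discard what is learned later. A careful site might record everything to day 90.

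This stands to the extent that the documents do not show that late events will be lost. It does not remove the conflict. Section 7.1.1 also refers to a protocol-specified reporting period, and Section 7.2.3 is the section that sets one. Where longer reporting was intended it was written out: Section 7.2.4 carries new malignancies through follow-up. No such sentence exists for immune-related events.

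A second reply is that the Safety Reporting Reference Manual (Appendix E), the IIR agreement and the IRB policy may set longer periods. They were not available. They could settle the external reporting of serious events, but nothing supplied shows that they govern the study's own recording of non-serious ones.

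A reader might also infer the size of the loss from the background data in Section 1.2.1. Two items tempt, and neither supports it.

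- *A death judged related to avelumab, 37 days after the last dose.* Section 1.2.1 places it in the context of lung cancer progression, does not call it immune-related and gives no onset date. If onset was by day 30, the event would have been inside capture and followed to its outcome.
- *The median of 11.7 weeks to first immune-related event.* This is 11.7 × 7 = 81.9 days from a starting point that is not stated. In the combination study (Section 1.4) avelumab was given for a median of 37.0 weeks, with a lower quartile of 14.0 weeks, or 14.0 × 7 = 98 days. If the 11.7 weeks run from first dose, roughly three quarters of those patients would still have been on treatment at that time. They had renal cancer, but this is the documents' only exposure figure for the combination.

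**Conclusion.** The inconsistency is real and should be corrected. Follow-up extends to day 90 after avelumab, every explicit capture window closes 30 days after the last dose, and the broader sentences conflict with those windows without overriding them. The main exposure is new non-serious immune-related events under Section 7.2.3.

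The gap is at most 60 days when Section 7.2.3 closes at day 30, and it shortens or vanishes for patients who stay on axitinib. That is a count of days, not of events. The documents give no rate of onset after the last dose, so the number of events affected cannot be derived. It would go too far to conclude that late serious events go unreported, or that a known share of immune toxicity is missed.

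The consequence is confined to the descriptive safety data. The response-rate design and the cycle-1 toxicity rule are unaffected. The day count assumes that the 30-day clock runs from the last dose of either drug. The view on serious events is provisional until the external documents are checked.

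**What to change.** Reconcile Section 5.3, footnote 7 to Table 6, and Sections 7.1.1 and 7.2.1 to 7.2.3 into one capture rule, placed in Section 7.2.3:

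- Capture serious events, and any adverse event that is or may be immune-related, found at the follow-up contacts already planned. Run this to 90 days after the last avelumab dose, or 30 days after the last dose of either drug if that is later.
- Leave the recording wording of Section 7.2.2 as broad as it is. Narrowing it could lose events not yet recognised as immune-related.
- Let capture for all adverse events reach at least the date of the actual safety visit, which may be day 37.
- Record the start date of new anticancer therapy and flag later events instead of dropping them.
- Use the same event window for the safety analysis in Section 9.1.
- Remove the second serious-event bullet in Section 7.2.1, whose start point conflicts with the first bullet and with Section 7.2.3.
- Check the rule against Appendix E, the IIR agreement and the IRB policy.

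The cost is an amendment to the wording, a longer eCRF entry window and a few more events to record, some of them confounded by later therapy. Sample size, error rates and treatment rules do not change.
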